#### **3.3.13 Study Milestones**

We propose to implement the study in three stages, with interim analyses and DSMB review after the first and second stages.

Stage 1: Following final protocol approval by all necessary authorities and procurement of necessary funding, staff will be trained, at least 4 pilot/training participants per site will be treated, and 20 participants will be randomized into the main trial across two sites (UNM and NYU, 10 per site). At the end of this stage, feasibility and tolerability will be assessed, and necessary protocol modifications may be made.

Stage 2: An additional 80 participants will be randomized, with the possible addition of one or two additional sites to enhance recruitment capacity. At the end of this stage, interim checks of attrition rates and the assumed error standard deviation  $\sigma$  for the primary outcome measure will be conducted to assess the adequacy of the projected study sample size. This check will be performed by an unblinded statistician, who will estimate the primary model, and report back on error variance and drop-out rates. Additional necessary protocol modifications may be made, and final sample size will be determined. In addition, safety interim looks will be performed (without formal statistical testing) at the regular DSMB meetings or unscheduled times per the DSMB's request. Although at this time we are not planning a formal statistical interim analysis for efficacy or futility, such an interim analysis can be performed if requested by the DSMB or the sponsor.

Stage 3: Assuming 180 participants are required, the 80 remaining participants will be randomized, with an additional 9 months to complete treatment and assessment of the final participants.

### **3.3.14 Regulatory Considerations**

#### **3.3.14.1 Statement of Compliance**

This trial will be conducted in compliance with the appropriate protocol, current Good Clinical Practice (GCP), the principles of the Declaration of Helsinki, and all other applicable regulatory requirements. Participating sites must obtain written approval of the study protocol, informed consent form, other supporting documents, and any advertising for participant recruitment from their local institutional review board (IRB) in order to participate in the study. Prior to study initiation, the protocol and the informed consent documents will be reviewed and approved by an appropriate Ethics Review Committee (ERC) or IRB. Any amendments to the protocol or consent materials must be approved before they are implemented. Annual progress reports and local Serious Adverse Event (SAE) reports will be submitted to each IRB, according to its usual procedures.

#### **3.3.14.2 Necessary approvals**

Human trials with Schedule I substances pose special challenges. The UNM site has already obtained an IND to study the use of psilocybin in the treatment of alcohol dependence, and has Schedule 1 DEA license and board of pharmacy approval to store, dispense, and administer psilocybin at UNM. The NYU site has an active Schedule I license to dispense psilocybin in the treatment of anxiety associated with cancer and will amend their Schedule 1 license for the purposes of this trial. The trial will not begin until the following have been achieved. 1) The existing UNM IND (#113080) will be amended to include the new protocol and the NYU site; 2) The existing DEA Schedule 1 licenses will be amended to include the new protocol; 3) any necessary local requirements, including Board of Pharmacy Schedule 1 permits, if necessary, will be obtained. Any additional sites will also satisfy these requirements prior to beginning participation in the study.

#### **3.3.14.3 Regulatory Files**

The regulatory files should contain all required regulatory documents, study-specific documents, and all important communications. Regulatory files will be checked at each participating site for the regulatory documents compliance prior to study initiation, throughout the study, as well as at the study closure.

#### **3.3.14.4 Health Insurance Portability and Accountability Act (HIPAA)**

Study sites may be required by their institutions to obtain authorization from participants for use of protected health information. Sites will be responsible for communicating with their IRBs or Privacy Boards and obtaining the appropriate approvals or waivers to be in regulatory compliance.

#### **3.3.14.5 Financial Disclosure**

All investigators will comply with the requirements of 42 CFR Part 50, Subpart F to ensure that the design, conduct, and reporting of the research will not be biased by any conflicting financial interest. Everyone with decision-making responsibilities regarding the protocol will have an up-to-date signed financial disclosure form on file.

### **3.3.14.6 Clinical Monitoring**

Site staff will be required to audit source documentation, including informed consent forms and HIPAA forms, regulatory documents and case report forms on a biannual basis. Site staff will be responsible for local quality assurance and will verify that study procedures are properly followed and that site staff are trained and able to conduct the protocol appropriately. If the site staff's review of study documentation indicates that additional training of study personnel is needed, this will be arranged as per the PI. Study team members will review each other's data for completeness, accuracy, and fidelity to the protocol.

### **3.3.14.7 Study Documentation**

Study documentation includes all case report forms, data correction forms, workbooks, source documents, monitoring logs and appointment schedules, sponsor-investigator correspondence, and signed protocol and amendments, Ethics Review Committee or Institutional Review Board correspondence, approved consent form, and signed participant consent forms. Source documents include all recordings of observations or notations of clinical activities and all reports and records necessary for the evaluation and reconstruction of the clinical research study. Whenever possible, the original recording of an observation should be retained as the source document; however, a photocopy is acceptable provided that it is a clear, legible, and an exact duplication of the original document.

## **3.3.15 Compensation to Participants**

Participants will be reimbursed \$50 for the screening visit, baseline visit, and each comprehensive visit (weeks 4, 8, 12, 24, 36, 38, 42 and 54), and \$20 for the interim visits 1 week after each drug administration session (weeks 5, 9 and 39). Participants completing all of the assessments would therefore receive a total of \$560.

## **4. HUMAN SUBJECTS PROTECTIONS**

### **4.1 Risks to Human Subjects**

#### **4.1.1 Human Subjects Involvement and Characteristics.**

##### **4.1.1.1 Participants**

Subjects will be women and men, age 25 to 65 with DSM-IV alcohol dependence, recruited from the community through advertisements at 2-4 sites. Participants will meet the inclusion and exclusion criteria listed in Section 3.3.6 of the protocol. Recruitment will continue until up to approximately 180 participants are randomized.

##### **4.1.1.2 Study treatments**

The proposed investigation is a multi-site, double-blind active-controlled trial (n = 180, 90 per group) contrasting the acute and persisting effects of psilocybin to those of diphenhydramine in the context of outpatient alcoholism treatment. The total duration of psychosocial treatment in the double blind period will be 12 weeks, and double-blind drug-administration sessions will occur after 4 and 8 weeks. The first psilocybin session will employ a moderately high dose of psilocybin (25 mg/70 kg). The dose may be increased in the second session to 30 mg/70 kg or 40 mg/70 kg, depending on response in prior sessions. The dose of diphenhydramine will start at 50 mg, and may be increased to 100 mg in the second session if 50 mg is well tolerated in the first session. Following completion of the double-blind period (34 weeks after randomization) all participants who meet interim safety criteria will be offered an additional session in which psilocybin will be administered. Drug administration will occur during 8-hour sessions conducted in an outpatient setting under close medical and psychiatric monitoring by two trained monitors. Psychosocial treatment will occur in the context of a behavioral intervention incorporating a modified version of the

Motivational Enhancement Therapy (Called Motivational Enhancement and Taking Action, META) [103] as well as preparation before and debriefing after the psilocybin session.

Procedures for minimizing COVID-19 risk among participants and study team members during required in-person visits (including routine temperature checks, use of personal protective equipment, symptom checks, etc.) are outlined in the COVID Safety Procedures SOP (etc-research-01\EtOH-14-00614\4. Study Documentation\3. SOPs\ SOP\_14-00614\_COVIDSafety\_Procedures\_V2\_09.01.2020.docx).

#### **4.1.2 Sources of Materials**

Materials obtained from participants will include samples of blood, urine, hair, fingernails, and breath. Data will be collected through use of interviews, questionnaires, physical examination, and laboratory tests. These data will include measures of medical health (medical evaluation), alcohol withdrawal, psychiatric diagnosis including drug and alcohol use disorders, substance use, alcohol consequences, motivation, self-efficacy, craving, mood and anxiety, acute effects of psilocybin administration, persisting effects of psilocybin administration, and safety. These materials and data will be obtained specifically for research purposes

#### **4.1.3 Potential Risks**

##### **4.1.3.1 Risks of experimental medications**

###### **4.1.3.1.1 *Psilocybin***

The test article used in the proposed study is psilocybin. In this study psilocybin will be used as the putatively active treatment. Psilocybin is a Schedule 1 substance with no currently accepted medical use. However, it has been used safely in numerous previous human studies, both in the US and abroad. In carefully conducted clinical research settings, with careful screening, preparation and support, the risks of psilocybin administration appear to be low [40, 41, 43, 97, 105]. Classic hallucinogens including psilocybin have the lowest physiological toxicity of all well-known drugs of abuse [163]. A recent analysis by the Independent Scientific Committee on Drugs in the UK found that individual and societal harms associated with use of psilocybin mushrooms were the lowest of any of the 20 drugs assessed [6]. However, there are some rare but potentially serious effects that require attention. With each exposure to psilocybin there is an additional chance that study participants may experience adverse events.

- Experiences with hallucinogens provoke a variety of positive and negative emotional responses in the hours to weeks following the acute drug experience, which can be unsettling. Anxiety and dysphoria are common during psilocybin intoxication. These symptoms can be distressing, and were the predominant emotional state in 4/36 sessions at 0.43 mg/kg reported by Griffiths et al. (2006). These symptoms generally respond well to reassurance. Anxiety rarely can escalate to panic.
- Increased blood pressure and heart rate during intoxication (mean increase of approximately 20 mm Hg systolic, 12 mm Hg diastolic, mean increase in pulse of approximately 10 bpm in Griffiths et al., 2006). This side effect is common, but unlikely to be clinically significant with careful screening for hypertension and cardiovascular disease.
- Serotonin syndrome is possible if psilocybin is used in combination with other serotonergic drugs. Individuals known to be taking such drugs will be excluded from the study. This adverse event is expected to be very uncommon.
- Transient psychotic symptoms (delusions, paranoia, hallucinations) have been reported during psilocybin intoxication. We are unaware of any reports of persistent psychotic symptoms associated with the use of psilocybin, but such symptoms have been reported following use of LSD [43, 164]. Individuals with history of psychosis or vulnerability (e.g., family history) are thought to be at higher risk for psychotic reactions to hallucinogens, but we cannot rule out a very small risk of such reactions to psilocybin in normal individuals.
- Secondary analyses of a pharmacokinetic study [165] revealed an association between psilocybin level increase in QTc (See Investigator Brochure v2.). at psilocin concentrations above 31.1 ng/ml.
- Hallucinogen persisting perception disorder can be caused by hallucinogen use. The incidence of this disorder is thought to be very low, and associated primarily with use of LSD [47].

- Headaches are common following psilocybin administration [109]. These headaches are not severe, resolve within a day, and appear to respond to over-the-counter pain medications.
- Psilocybin, like other classic hallucinogens, is not reliably reinforcing in humans or in animal models used to study addiction potential [46]. However, psilocybin is an abusable drug. It is theoretically possible that a participant could develop a pattern of psilocybin misuse due to his/her experience in the trial, although this has not been reported in previous studies in which psilocybin or other classic hallucinogens have been administered to humans.

Although there is considerable clinical experience with psilocybin over more than 50 years, it has not been used in controlled trials with alcohol dependent subjects. There is, however, a large literature dating from the 1950s through the early 1970s, including over 1000 subjects, on the use of LSD in the treatment of alcoholism [1, 11-15, 21-26]. Few safety issues were noted in these studies.

#### 4.1.3.1.2 Diphenhydramine

Diphenhydramine is used as an active control medication in this study. Diphenhydramine is a H1 antagonist (antihistamine) which is available over the counter and by prescription for treatment of insomnia, allergic reactions, parkinsonism, and motion sickness. It has been safely administered in doses up to 400 mg PO [114-116, 166]. Reported side effects and adverse events associated with diphenhydramine include the following (from package insert [167]).

- *General*: Urticaria, drug rash, anaphylactic shock, photosensitivity, excessive perspiration, chills, dryness of mouth, nose and throat.
- *Cardiovascular System*: Hypotension, headache, palpitations, tachycardia, extrasystoles.
- *Hematologic System*: Hemolytic anemia, thrombocytopenia, agranulocytosis.
- *Nervous System*: Sedation, sleepiness, dizziness, disturbed coordination, fatigue, confusion, restlessness, excitation, nervousness, tremor, irritability, insomnia, euphoria, paresthesia, blurred vision, diplopia, vertigo, tinnitus, acute labyrinthitis, neuritis, convulsions.
- *GI System*: Epigastric distress, anorexia, nausea, vomiting, diarrhea, constipation.
- *GU System*: Urinary frequency, difficult urination, urinary retention, early menses.
- *Respiratory System*: Thickening of bronchial secretions, tightness of chest and wheezing, nasal stuffiness.

#### 4.1.3.1.3 Adjunctive medications

With the exception of acetaminophen and ibuprofen, use of these medications is expected to occur uncommonly if at all in this study.

- For treatment of severe hypertension: captopril 25mg orally or sublingually; clonidine Orally, initial 0.1mg; may be followed by additional doses of 0.1 mg every hour, if necessary, to a maximum total dose of 0.7 mg. Hydralazine orally, 10mg once. Common side effects include headache, lightheadedness, dizziness, flushing, orthostatic hypotension, and reflex tachycardia. Uncommon but serious reactions include severe hypotension, paradoxical bradycardia angioedema and allergic reactions.
- For severe anxiety: Diazepam 5-10 mg orally or Lorazepam 1 mg intramuscularly. The most common effects of benzodiazepines are sedation, dizziness, weakness, and unsteadiness. Rare but serious adverse events that could occur with a single administration include respiratory depression, apnea, and anaphylaxis.
- Olanzapine 5-10 mg orally or intramuscularly for psychotic symptoms (delusions, hallucinations, disorganized behavior) that pose a significant danger. Common side effects of olanzapine possible with one or two doses are somnolence, dizziness, hypotension, akathisia, extrapyramidal symptoms, dry mouth, tremor, nausea, and vomiting. Rare but serious side effects include seizures, neuroleptic malignant syndrome and tardive dyskinesia, (the latter two are extremely unlikely with one or two small doses). The risk of hypotension is increased when intramuscular olanzapine is given in combination with benzodiazepines, so intramuscular olanzapine will not be given if diazepam has already been administered.

- For headache or pain: Acetaminophen 500-1000 mg orally q4 hours prn pain/headache and/or Ibuprofen 600 mg-800 mg orally x q8 prn pain/headache. Common side effects include nausea, stomach discomfort.

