Monitoring and Safety Procedures. As psilocybin use is associated with a small risk of emesis, participants will be instructed to have only a light breakfast on the morning of the psilocybin administration sessions, at least an hour before the beginning of the session. Participants will complete assessments including confirmation of medical stability and drug- and alcohol-free status. (If the participant has CIWA-Ar score of 7 or greater, need for detoxification will be assessed and the patient will be referred for treatment if indicated). They will then ingest the capsule containing the study medication, followed by approximately 4 ounces of water. Participants will remain under observation for at least 8 hours following psilocybin administration (maximal effects are expected to occur at approximately 2-3 hours). Two therapists will be present throughout all psilocybin administration sessions (except for breaks, which will be taken one at a time). Interaction with the participants will be supportive and non-directive. Vital signs will be monitored by study staff at 30 minute intervals for three hours, and then hourly. At the time of vital sign measurement, the therapists will also check in with briefly with participants and complete a brief Monitor Rating Questionnaire. Management of hypertension will be as follows. If BP is greater than or equal to 180 systolic or 100 diastolic, subjects will be assessed for discomfort that may be causing the BP elevation, e.g. anxiety, headache/pain, or alcohol withdrawal. These symptoms should be addressed/medicated, and BP will be reassessed at 15 minute intervals until below 180/100. If patient has >2 BP readings of 200/110 or higher, then the BP will be treated directly. At this time, the patient should specifically be assessed for new chest pain, shortness of breath, or focal weakness, in which case the subject will need more urgent medical attention. The following medications will be available for administration by the study physician if needed to treat hypertension (captopril 25 mg orally/sublingually, clonidine 0.1 mg orally, or hydralazine 10 mg orally). In the event that a subject experiences distressing anxious or psychotic symptoms during the experimental or control session, the clinical personnel in attendance will initiate verbal communication designed to reorient and reassure the subject. If that does not effectively alleviate the signs of an anxious or psychotic reaction, diazepam 5-10 mg, orally, or lorazepam 1 mg, intramuscularly, will be administered to lower anxiety. Only if that is ineffective or if the participant presents a danger to self or others will an antipsychotic be administered, olanzapine 5-10 mg, given either orally or intramuscularly. For headache or pain, Tylenol 500-1000 mg and/or Ibuprofen 600 mg-800 mg may be administered once orally.

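### Intramuscular olanzapine is barred only after diazepam, although the stated reason covers benzodiazepines generally and the protocol also offers intramuscular lorazepam

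*Combined protocol and SAP*

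**What the plan says.** Section 4.1.3.1.3 (Adjunctive medications) lists the rescue drugs. For severe anxiety it gives "Diazepam 5-10 mg orally or Lorazepam 1 mg intramuscularly. The most common effects of benzodiazepines are sedation", so both drugs are described together as benzodiazepines. Under olanzapine it gives the hazard, "The risk of hypotension is increased when intramuscular olanzapine is given in combination with benzodiazepines", and draws the rule from it: the risk is raised "in combination with benzodiazepines, so intramuscular olanzapine will not be given if diazepam has already been administered". Leaving aside acetaminophen and ibuprofen, the section says that "use of these medications is expected to occur uncommonly if at all in this study".

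The Monitoring and Safety Procedures paragraph of Section 3.3.8.1.3 gives the order of steps in a session. If reassurance does not settle distressing anxious or psychotic symptoms, "diazepam 5-10 mg, orally, or lorazepam 1 mg, intramuscularly, will be administered to lower anxiety". Then comes the antipsychotic step, whose condition is "Only if that is ineffective or if the participant presents a danger to self or others". Once that condition is met, the route is left open: "will an antipsychotic be administered, olanzapine 5-10 mg, given either orally or intramuscularly". No limit linked to a benzodiazepine is stated there.

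Section 4.2.2.1, item f (Planning for emergencies), lists the same drugs, doses and routes, also without a limit. It adds that referral for emergency treatment or hospital admission is available at each site.

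**The concern.** A prohibition introduced as the consequence of a hazard should reach every drug that the protocol itself places under that hazard. This one reaches diazepam and omits lorazepam, the only other benzodiazepine supplied. A clinician who follows the text exactly could give lorazepam by injection, find it ineffective, and then give olanzapine by injection. The protocol warns about that pairing and does not bar it.

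The omitted drug may also be the more relevant one. A participant given lorazepam by injection may be someone who cannot or will not swallow diazepam, and that participant is more likely to need olanzapine by injection too. This is an inference; the documents do not say it.

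What is at stake is the handling of an acute reaction during a session. The trial's inference is not involved.

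**Working it through.** No arithmetic applies, and the plan has no figure to reproduce. The check sets the rule beside its reason and beside every other place that gives these drugs.

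| Place | Benzodiazepines offered | Olanzapine route | Limit on intramuscular olanzapine |
|---|---|---|---|
| 4.1.3.1.3, stated reason | the class (diazepam and lorazepam listed) | intramuscular | warning covers the class |
| 4.1.3.1.3, rule | as above | oral or intramuscular | barred after diazepam only |
| 3.3.8.1.3, session procedure | diazepam oral or lorazepam intramuscular | oral or intramuscular | none stated |
| 4.2.2.1 item f | diazepam oral or lorazepam intramuscular | oral or intramuscular | none stated |

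1. Is lorazepam within the reason? Yes. Section 4.1.3.1.3 calls both anxiety drugs benzodiazepines, and the reason refers to benzodiazepines without qualification. No outside pharmacology is needed.

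2. Is lorazepam within the rule? No. The rule's condition is prior diazepam. Of the two benzodiazepines that may precede olanzapine, one triggers the bar and one does not.

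3. Is the gap closed elsewhere? Not in the documents supplied. Sections 3.3.8.1.3 and 4.2.2.1 list the drugs without a limit. Section 4.1.3.1.4 mentions benzodiazepines and olanzapine only for pregnancy and lactation.

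4. Can the gap be reached? Yes. The session procedure goes from reassurance to a benzodiazepine, and then to olanzapine if that fails or the participant is dangerous. Choosing lorazepam at the second step and the injection at the third gives intramuscular lorazepam followed by intramuscular olanzapine. Sections 4.1.3.1.3 and 4.2.2.1 describe olanzapine as for psychotic symptoms that pose a danger. That narrower indication still allows the sequence.

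5. Does the diazepam bar hold during a session although Section 3.3.8.1.3 does not repeat it? Yes. Both sections belong to one protocol, so a limit stated once applies throughout.

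**The case against.** The strongest reply is that no two statements conflict. The sentence containing the bar also carries the class warning, so anyone who reads it is told that lorazepam raises the risk too. The protocol does not say in terms that intramuscular olanzapine may follow lorazepam; it only fails to forbid it. This stands as a description: the rule is under-inclusive rather than contradicted. It does not remove the gap, because the sponsor judged the hazard to warrant a prohibition and the prohibition stops short of its own reason.

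A second reply is that the event is unlikely and supervised. Use of the drugs is expected to be rare, olanzapine is a late step, and an oral form is available. Section 3.3.8.2.3 requires a physician among the two therapists, and Section 3.3.8.1.3 says "Vital signs will be monitored by study staff at 30 minute intervals for three hours, and then hourly". All of this stands and keeps the point minor. Monitoring may help detect hypotension, but it does not complete the rule.

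A third reply is that the site emergency SOPs (Section 3.3.8.1.3) or the Therapy Manual, cited for session vital signs in Section 3.3.10.9, may already carry a wider bar. They are not among the documents, so this cannot be excluded. The protocol text would still need to match them.

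Two stronger readings are tempting. A reader might infer that the protocol should also forbid a benzodiazepine after intramuscular olanzapine, since combination does not imply an order and a dangerous participant may receive olanzapine before any benzodiazepine. The documents do not support going that far. No section describes giving a benzodiazepine after olanzapine, and a flat ban would be a new clinical policy resting on a sentence that says only that risk is increased. A reader might also treat the silence of Section 3.3.8.1.3 as an error. It is not, for the reason given in step 5 of the working.

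**Conclusion.** The point holds as a gap between one rule and its stated reason. The bar should cover lorazepam and does not, and the written session procedure permits intramuscular lorazepam followed by intramuscular olanzapine.

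Its size is small. One of the two benzodiazepines is left out; that describes the wording and does not measure risk. The documents give no event rate and no magnitude for the hypotension hazard, so the number of participants affected cannot be estimated.

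The conclusion assumes that the rule was meant to follow from the reason, as the sentence's own structure indicates. It also assumes that the documents supplied contain every limit the protocol states. Confidence in the textual gap is high. Its practical effect is uncertain because the SOPs and the Therapy Manual were not available.

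**What to change.** In Section 4.1.3.1.3, change the condition for withholding intramuscular olanzapine from prior diazepam to prior administration of *any benzodiazepine (diazepam or lorazepam)*. Check that the site emergency SOPs and the therapy manual say the same. Optionally, add a pointer to Section 4.1.3.1.3 at the olanzapine step in Section 3.3.8.1.3, where staff will look during a session.

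The administrative cost is a protocol amendment replacing one phrase, plus the document check. Data collection and analysis do not change.

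The clinical cost is the loss of intramuscular olanzapine after intramuscular lorazepam. This matters most for a participant who cannot take oral medication, for whom oral olanzapine may not be workable either and emergency referral would be the remaining route. The sponsor should accept that trade-off knowingly when making the change.

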*d. Support during psilocybin sessions:* Because this study involves use of psilocybin in a clinical population as part of an intervention intended to be therapeutic, the two study therapists will serve as the monitors who will attend the patient during the psilocybin sessions. At least one of these therapists will be a licensed clinician.

*e. Physical environment:* The psilocybin session will take place in outpatient facilities that are appropriate for hallucinogen administration sessions. To the extent possible, the room used for the session will be specially prepared for the sessions to provide a warm and home-like rather than a stark clinical quality because of the large influence that setting can have on the subjective effects of hallucinogens. Each site will have detailed SOPs in place for managing medical or psychiatric emergencies should any occur.

*f. Planning for emergencies:* Each of the research sites has established practices for managing medical and psychiatric emergencies, and the study staff will continue to utilize these procedures. Staff will be responsible for monitoring participants for possible clinical deterioration or other problems, and for implementing appropriate courses of action. Acute adverse reactions to psilocybin initially will be managed by increasing psychological support ("talking down"). Medications will be available for administration if needed to treat hypertension (sublingual captopril 25 mg orally/sublingually, clonidine 0.1 mg PO, and hydralazine 10 mg PO), anxiety (diazepam 5-10 mg PO, or lorazepam 1 mg IM), or acute psychosis posing a danger to the participant or others (olanzapine 5-10 mg PO or IM). Referral for emergency treatment and/or hospitalization will be available at each site. A study clinician will be available by pager or phone at all times during study participation.

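### The limit on intramuscular olanzapine names only diazepam, although its stated reason covers benzodiazepines and intramuscular lorazepam is the other one permitted

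*Combined protocol and SAP*

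**What the plan says.** Three sections of the protocol deal with the rescue drugs for anxiety and psychosis.

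- **Section 4.1.3.1.3 (Adjunctive medications)** lists the benzodiazepines: "For severe anxiety: Diazepam 5-10 mg orally or Lorazepam 1 mg intramuscularly". Under olanzapine it gives a hazard, "The risk of hypotension is increased when intramuscular olanzapine is given in combination with benzodiazepines", and a rule that follows from it, "so intramuscular olanzapine will not be given if diazepam has already been administered". Apart from acetaminophen and ibuprofen, it says that "use of these medications is expected to occur uncommonly if at all in this study".
- **Section 3.3.8.1.3 (Dosing and Administration, under Monitoring and Safety Procedures)** sets the order of steps during a session. Verbal reassurance comes first. If that fails, "diazepam 5-10 mg, orally, or lorazepam 1 mg, intramuscularly, will be administered to lower anxiety". Then: "Only if that is ineffective or if the participant presents a danger to self or others will an antipsychotic be administered". The drug is olanzapine 5-10 mg, by mouth or intramuscularly.
- **Section 4.2.2.1, item f (Planning for emergencies)** lists the same options, including "anxiety (diazepam 5-10 mg PO, or lorazepam 1 mg IM", and olanzapine by either route.

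The limit on intramuscular olanzapine appears only in the first of these sections.

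**The concern.** The reason and the rule sit in the same sentence but do not have the same scope. The reason covers benzodiazepines; the rule covers diazepam. Lorazepam is the other benzodiazepine in the protocol, listed in all three sections and given by injection.

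Staff could therefore follow the written rule exactly and still give the combination whose risk the protocol itself names. The person exposed would be a participant in acute distress whose first rescue drug had not worked.

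The open sequence is also a plausible one. A participant who cannot or will not swallow a tablet would probably be given lorazepam, the only injectable benzodiazepine listed, and for the same reason would next be considered for injectable olanzapine. This is an inference, since the protocol gives no rule for choosing between the two benzodiazepines.

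**Working it through.** There is no stated figure to reproduce. The check is a comparison of wording, followed by a count.

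**1. Find every relevant statement.** Olanzapine, diazepam, lorazepam or benzodiazepines are mentioned in sections 3.3.8.1.3, 4.1.3.1.3, 4.1.3.1.4 and 4.2.2.1. Section 4.1.3.1.4 concerns only pregnancy and lactation, which leaves the three sections quoted above.

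**2. Compare the scope of the hazard with the scope of the rule (section 4.1.3.1.3).**

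| Element | Drugs covered |
|---|---|
| Stated hazard with intramuscular olanzapine | Benzodiazepines as a class |
| Benzodiazepines permitted for severe anxiety | Oral diazepam; intramuscular lorazepam |
| Rule withholding intramuscular olanzapine | Diazepam only |

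**3. Follow the session procedure (section 3.3.8.1.3).** It runs from reassurance, to diazepam or lorazepam, to olanzapine by either route. Two benzodiazepine-first sequences can end in intramuscular olanzapine:

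| Sequence | Barred by the written rule? |
|---|---|
| Oral diazepam, then intramuscular olanzapine | Yes |
| Intramuscular lorazepam, then intramuscular olanzapine | No |

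**4. Look for a limit elsewhere.** Neither section 3.3.8.1.3 nor section 4.2.2.1 adds one for lorazepam.

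**5. Count.** Sequences: 2 benzodiazepines × 1 order = 2. Barred as written: 1 of 2. Barred if the rule named both drugs: 2 of 2.

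The count describes what the wording allows. The documents give no rate of rescue use, of hypotension or of the choice between the two benzodiazepines, so it cannot be turned into a risk.

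**The case against.** The strongest reply is that a clinician would not be misled. The warning about benzodiazepines stands in the same sentence as the rule, and the entry just before it discusses both drugs under that class name. Section 3.3.8.2.3 calls for a physician among the therapists at all sessions. On this view the clause is a drafting slip whose intent is plain. That is probably how it arose, but an emergency limit should not rest on inference. The safeguard is also stated less firmly in section 4.2.2.1, item d, which promises only a licensed clinician. Site emergency procedures and the therapy manual may contain a fuller limit. They are not among the documents, and they would not correct the protocol text.

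The reply on severity largely stands. The open sequence needs failed reassurance, a choice of lorazepam, failure of lorazepam, and then a choice of the injection over oral olanzapine. Section 3.3.8.1.3 has vital signs taken every 30 minutes for three hours and then hourly, with at least 8 hours of observation, so hypotension would be looked for.

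Three stronger readings may tempt a reader, and the documents do not support them.

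- **That only 1 of 4 combinations is barred.** This counts both orders. The danger trigger in section 3.3.8.1.3 can bring olanzapine in first, but no section describes a benzodiazepine as the step after it. Those two cells come from silence and not from a described pathway.
- **That the session procedure and the emergency plan contradict the limit.** They do not repeat it, but nothing suggests that they override it. Section 4.1.3.1.3 applies throughout the protocol.
- **That the two drugs should never be given in the same session, in either order.** The protocol states a raised risk, with no rate, dose relation or time window. Whether a benzodiazepine should be withheld after intramuscular olanzapine is a clinical judgement that the text does not settle.

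**Conclusion.** The point holds in a narrow form. The rule in section 4.1.3.1.3 is narrower than its own rationale: it closes one of the two benzodiazepine-first sequences to intramuscular olanzapine and leaves the lorazepam sequence open.

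This rests on the protocol text alone and takes the sponsor's own statement of the hazard as given. It assumes no outside pharmacology. It does not assume that the combination has been or will be given, and actual exposure cannot be judged without the site procedures.

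Severity is minor. Use is expected to be rare, and the point bears on participant safety. No event rate, imbalance between arms or effect on the drinking analyses is claimed.

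**What to change.** In section 4.1.3.1.3, change the condition so that intramuscular olanzapine is withheld once any benzodiazepine (diazepam or lorazepam) has been given. This alone closes the gap.

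As a helpful option, add a short cross-reference to the limit in section 3.3.8.1.3 and in section 4.2.2.1, item f, where staff would look during a session.

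The administrative cost is a wording amendment, which section 3.3.14.1 requires to be approved before it is implemented. The clinical cost is that intramuscular olanzapine is no longer available after intramuscular lorazepam. In a rare emergency that leaves oral olanzapine or, if the participant cannot take it, the emergency referral provided for in section 4.2.2.1. Intramuscular olanzapine remains available under the danger trigger when no benzodiazepine has been given.
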